3.1 Entecavir (ETV)

a. PHARMACOLOGY

Mechanism of Action:

Entecavir is a guanosine nucleoside analogue. The phosphorylated active form inhibits the activity of hepatitis B virus (HBV) polymerase in base priming, reverse transcription of the negative strand pregenomic messenger RNA, and synthesis of the positive strand of HBV DNA.

b. PHARMACOKINETICS

1. Absorption:

The peak plasma concentration (C_{max}) of entecavir is achieved in 0.5 to 1.5 hours at doses ranging between 0.1 and 1 mg, and the steady state is achieved in 6 to 10 days. Both C_{max} and area under the concentration-time curve (AUC) at steady state increases proportionally to increasing doses of entecavir. The oral tablet and the oral solution have a bioavailability ratio of 1:1 and may be used interchangeably.

Co-administration of entecavir with food has been shown to delay absorption, decrease C_{max} by 44 to 46%, and decrease AUC by 18 to 20%. Entecavir should be administered at least 2 hours before or after a meal.

2. Distribution:

Pharmacokinetic studies have shown that entecavir distributes extensively into tissues and have an approximate protein binding of 13%.

3. Metabolism:

Entecavir is not metabolized by the cytochrome P450 enzymes, and it does not inhibit or induce the P450 enzymes.

4. Elimination:

Entecavir is mainly eliminated by the kidneys as 62 to 73% unchanged drug through glomerular filtration and net tubular secretion. The half-life of entecavir is approximately 128 to 149 hours, and the renal clearance ranges between 360 to 471 mL/min.

c. ADVERSE EFFECTS

1. Possible Side Effects of *Entecavir*:

Refer to the current FDA-approved package insert for the most comprehensive and up to date information on adverse reactions.

Adverse effects reported in > 10% of subjects treated with entecavir include elevated alanine aminotransferases.

Adverse effects reported in 1% to 10% of subjects include: headache, fatigue, skin rash, hematuria, glycosuria, hyperglycemia, abdominal pain, nausea, vomiting, diarrhea, unpleasant taste, elevated serum lipase, bilirubin, and creatinine.

Serious adverse effects reported in < 1% of subjects include: anaphylactoid shock, hepatomegaly with steatosis, lactic acidosis, macular edema, and thrombocytopenia.

2. Pregnancy and Lactation:

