7.2 Cohort 1 - Chronic HBV Anti-Viral Treatment

a. Arm 1: Prophylactic Anti-Viral Therapy

The treating investigator and patient will choose the appropriate anti-viral therapy from one of the three anti-viral therapies below. Patients may initiate anti-viral therapy with a reduced dose based on creatinine clearance (see Dose Modifications, [Section 8.2](#))

Start anti-HBV treatment before anti-cancer therapy or up to 42 days after initial anti-cancer therapy. Continue anti-HBV treatment for 6 months after last dose of anti-cancer therapy or for up to 24 months after registration, whichever occurs first.

Agent	Dose	Route	Start Day	Schedule
Tenofovir alafenamide (TAF)	25 mg ^A	PO ^B	As soon as possible after registration; before or up to 42 days after initial dose of anti-cancer therapy	Daily for up to 6 months after the last dose of anti-cancer therapy or maximum of 24 months ^C
Tenofovir disoproxil fumarate (TDF)	300mg PO		As soon as possible after registration; before the last dose or up to 42 days after initial dose of anti-cancer therapy	Daily for up to 6 months after the last dose of anti-cancer therapy or Maximum of 24 months

Entecavir (ETV)	0.5mg	As soon as possible after registration; before the last dose or up to 42 days after initial dose of anti-cancer therapy or anti-cancer therapy.	Daily for up to 6 months after the last dose of anti-cancer therapy or Maximum of 24 months.
--------------------	-------	---	--

^A In patients taking carbamazepine the TAF dose will be increased to 50 mg daily.

^B See dosage administration details in [Section 3.1d](#).

^C Note: Chronic HBV patients should not abruptly stop antiviral therapy after 24 months. Please see [Section 8.2](#) for details on cessation of anti-HBV therapy in chronic HBV patients.

b. Arm 2: Upon Indication Anti-Viral Therapy

The treating investigator and patient will choose the appropriate anti-viral therapy from one of the three anti-viral therapies below. Patients may initiate anti-viral therapy with a reduced dose based on creatinine clearance (see Dose Modifications, [Section 8.2](#)).

Monitor ALT at least every 4 weeks (+/- 2 weeks) as part of trial monitoring for the first 24 weeks, then every 8 weeks thereafter. If hepatitis flare occurs (see definition for hepatitis flare in [Section 10.2b](#)), then obtain an HBV DNA test per usual care. Start anti-HBV therapy if HBV reactivation occurs.

Agent	Dose	Route	Start Day	Schedule

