13.0 REGISTRATION GUIDELINES

13.1 Registration Timing

Patients must be registered ≤ 28 days prior to initial anti-cancer therapy. If the patient has already started systemic anti-cancer therapy, patient must be registered ≤ 42 days after the initiation of first cycle of anti-cancer therapy.

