15.0 SPECIAL INSTRUCTIONS

15.1 Blood Serum Specimens (REQUIRED)

Specimens for translational medicine and banking (submitted to the Biospecimen Bank – Solid Tissue, Myeloma and Lymphoma Division, Lab #201) required for patient:

- a. Blood serum for HBV DNA, HBsAg, ultrasensitive HBsAg, anti-HBs, HBV RNA, HBV core-related antigen (HBcrAg) testing and serum cytokine analysis must be submitted at the following time points (see [Section 9.0](#)):
 1. At the time of registration (+/- 4 weeks)
 2. Every 8 weeks (+/- 2 weeks) from date of registration
 3. At time of HBV re-activation
- b. At each time point, 10 mL of blood will be drawn into red top tube(s) using institutional supplies, spun down at 1500 G for 10 minutes at room temperature, and serum aliquoted into 1 mL aliquots. Serum should be stored in a -70 to -80°C freezer (preferred, if available). Samples stored in a -70 to -80°C freezer may be batch shipped. If batch shipped, samples must be shipped within 3 months of collection.

If -70 to -80°C freezer is not available, then ship immediately on dry ice (ship overnight Monday – Thursday), or store in a -20°C to -80°C freezer and ship within 2 weeks, noting the storage temperature in the Specimen Tracking System.

Samples must be shipped (Monday – Thursday) on dry ice by overnight shipping for receipt Tuesday - Friday. Samples should not be shipped prior to a holiday. The SWOG Biospecimen bank is not able to receive frozen samples on Saturdays, Sundays, or holidays. See [Section 15.3](#) for specimen shipment instructions.

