15.2 Whole Blood Specimens (**OPTIONAL for Patient**)

- a. With patient's consent whole blood specimens for intracellular cytokine staining (ICC), ELISA, IFN-gamma elispot testing (submitted to the SWOG Biospecimen Bank – Solid Tissue, Myeloma, and Lymphoma Division, Lab #201) must be submitted at the following time points (see [Section 9.0](#)).
 1. At time of registration (+/- 4 weeks)
 2. 8-12 weeks from registration
 3. 24 weeks (+/- 4 weeks) from date of registration
 4. At time of HBV-re-activation
- b. At each time point, a total 50 mL of blood will be drawn into five to eight purple top (EDTA) tubes using institutional supplies. Blood should be shipped the day of collection, overnight at ambient temperature. Blood may be shipped on Monday through Friday for Tuesday through Saturday delivery. If shipping for Saturday delivery, please mark Saturday delivery and notify the Bank. See [Section 15.3](#) for specimen shipment instructions.

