18.1 Translational Medicine

HBV DNA, HBsAg, ultrasensitive HBsAg, anti-HBs, HBV RNA, HBV core-related antigen (HBcrAg)

Blood specimens for 444 study participants enrolled in the main clinical study will be collected at baseline and at regular intervals after registration as outlined above in [Section 9.0](#) Study Calendar and [Section 15.0](#). Sixty sites will enroll 222 chronic HBV and 222 past HBV patients, collect blood specimens at study time points, and send specimens to the SWOG Biospecimen Bank. The SWOG Biospecimen Bank will prepare and batch-ship specimens to Toronto Centre for Liver Disease Laboratories during the main clinical study for research tests (HBV DNA, HBsAg, ultrasensitive HBsAg, HBV RNA, HBcAg, anti-HBs, and HBeAg tests) to retrospectively identify patients with HBV reactivation. The results from labs at Toronto Centre for Liver Disease will be used to determine cases of HBV reactivation and matched controls.

a. Specimen Collection and Processing:

Specimens for the TM studies will be collected in red top tubes at 5 time points (+/- 4 weeks) and processed at the site as detailed in [Section 15.0](#).

See Section 18.1d for SWOG Biospecimen Banking Instructions

At the end of the study, the bank will ship specimens to The Toronto Centre for Liver Disease labs where the following HBV tests will be performed: HBV DNA, HBsAg, ultrasensitive HBsAg, HBV RNA, HBcAg, anti-HBs, and HBeAg tests. ALT, total bilirubin, and INR will be performed as part of routine monitoring in the main clinical study SWOG [S1614](#).

b. **Translational Aim 1. To determine baseline and changes in overall immune status and HBV-specific immune response in solid tumor patients with chronic or past HBV infection receiving anti-cancer therapy, and to compare the differences in these immune responses by HBV reactivation status.**

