HBV-specific T cell and B cell responses are weak in patients with chronic HBV infection. However, evidence from patients receiving immunosuppressive therapy confirms that there is ongoing immune control in chronic HBV infection. Multiple agents with different immunosuppressive and/or immunomodulatory properties have been associated with HBV-reactivation. Reactivation occurs with non-specific therapy like corticosteroids, as well as with targeted treatments like B cell-depleting agents and anti-TNF therapies. Therefore, perturbation of immune composition and/or specific antiviral pathways can result in reactivation. However, HBV reactivation does not occur in all patients who receive immunomodulatory therapies. We hypothesize that the composition, phenotype and function of immune cells at baseline will predict HBV reactivation after starting anti-cancer chemotherapy.

Aim 2 will conduct a case-control study comparing immune status in patients who develop HBV reactivation during chemotherapy with a 1:1 matched set of controls who were not on anti-HBV therapy and did not develop HBV reactivation. Specimens will be collected at the time points detailed in [Section 9.0](#) Study Calendar and [Section 15.0](#). Participants who are clinically diagnosed to have HBV reactivation will have an additional blood draw for future immune studies. All blood specimens will be collected from 444 study participants then shipped overnight to SWOG Biospecimen Bank for processing and storage in a -80°C freezer. Specimens will be sent from SWOG Biospecimen Bank to Drs. [name] and [name]'s laboratory at the Toronto Centre for Liver Disease for immune

studies detailed below. [name] and her immunology collaborators will have priority access to the specimens at SWOG Biospecimen Bank at all times.

The samples are the key novel aspect of the study. Using data from Translational Aim 1, we will identify patients with reactivation defined by increasing HBV viral load with an equal number of patients not experiencing HBV reactivation after treatment. The primary analysis will be performed on longitudinal samples comparing change from baseline upon starting chemotherapy in HBV reactivation patients and those without reactivation. Patients will be matched by age (5-year strata), sex, type of anti-cancer therapy (cytotoxic, immune or targeted) and chronic vs. past HBV.

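### First serum and whole-blood samples may be drawn up to four weeks after registration with no tie to a first dose, so some baseline values in the translational analyses may be on-treatment

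*Combined protocol and SAP*

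**What the plan says.** **Sample timing.** The required serum sample is timed "At the time of registration (+/- 4 weeks" (Section 15.1) and the optional whole blood "At time of registration (+/- 4 weeks" (Section 15.2). Section 18.1 repeats a four-week tolerance for the translational specimens. Section 14.4a lists the Section 15 specimens among items due within 15 days of registration. The calendar's general two-week tolerance yields wherever another window is specified.

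**Treatment timing.** Arm 1 antivirals start "As soon as possible after registration; before or up to 42 days after initial dose of anti-cancer therapy" (Section 7.2a). For entecavir, "the steady state is achieved in 6 to 10 days" (Section 3.1). On registration, Section 13.1 says "Patients must be registered ≤ 28 days prior to initial anti-cancer therapy"; for those already on therapy, "patient must be registered ≤ 42 days after the initiation of first cycle of anti-cancer therapy".

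**Use of the samples.** Section 18.1 hypothesises that the "composition, phenotype and function of immune cells at baseline will predict HBV reactivation after starting anti-cancer chemotherapy" and makes change from baseline its primary analysis. It also states: "The results from labs at Toronto Centre for Liver Disease will be used to determine cases of HBV reactivation and matched controls".

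**Other baseline tests.** Section 5.3b requires an HBV DNA result within 42 days before registration, and Section 5.3a requires HBsAg, anti-HBc and anti-HBs within 28 days. Section 5.2f excludes patients on HBV antivirals at entry.

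**The concern.** A baseline biomarker should describe the patient before the exposure under study. Here the window is centred on registration, which fixes neither the first antiviral dose nor the first anti-cancer dose. Two exposures can therefore enter the first sample:

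- **Antiviral.** This applies by design to Arm 1 and not to Arm 2, the other arm of Cohort 1.
- **Anti-cancer therapy.** This can apply in any arm, with no built-in difference between arms.

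If on-treatment samples are pooled with pre-treatment ones, a baseline predictor partly measures early response to treatment, and change from baseline starts from a different point in each patient. HBV RNA, HBcrAg, ultrasensitive HBsAg, cytokines and immune-cell markers have no second pre-treatment measurement to fall back on.

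**Working it through.** **The plan's own figure.** The case-control study expects 44 reactivation cases: 2 cohorts × 111 standard-arm patients × 20% = 44.4. This reproduces. Nothing here disputes it or any other sample-size figure.

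**Inputs.** Draw window −28 to +28 days from registration (15.1, 15.2). Registration from 28 days before to 42 days after the start of anti-cancer therapy (5.2c, 13.1). Entecavir steady state at 6 to 10 days (3.1). Submission deadline 15 days (14.4a).

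**1. Draw relative to the start of anti-cancer therapy (day 0).**
- Earliest: −28 − 28 = day −56.
- Latest: 42 + 28 = day 70, of which 42 days come from eligibility and 28 from the draw window.
- Latest if the 15-day deadline binds: 42 + 15 = day 57.
- A patient registered 28 days before therapy and drawn at +28 is at 28 − 28 = day 0.

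**2. Antiviral exposure at the draw, Arm 1.**
- Maximum, if the drug starts on the day of registration: 28 days, or 15 if the deadline binds.
- On entecavir, days beyond steady state at a +28 draw: 28 − 10 = 18 to 28 − 6 = 22.
- At a +15 draw: 15 − 10 = 5 to 15 − 6 = 9.

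**3. Spacing to the next sample.**
- Serum: the earliest week-8 draw is 56 − 14 = day 42, so the gap can be as short as 42 − 28 = 14 days.
- Whole blood, due at 8 to 12 weeks: the gap runs from 8 − 4 = 4 weeks to 12 + 4 = 16 weeks.

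**4. Which analyses are reached (Sections 18.1 and 10.2a).**

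| Analysis | Population | Exposure that can enter the baseline sample |
|---|---|---|
| Immune case-control | Standard arms only; controls not on anti-HBV therapy | Anti-cancer therapy |
| Cox predictor models | All 222 patients per cohort | Anti-cancer therapy; in Cohort 1 also Arm 1 antiviral |
| Clinical reactivation, 2-log rule | Both arms of each cohort | Depends on which HBV DNA value is the baseline, which 10.2a does not state |

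The documents do not label Arm 2 as the standard arm of Cohort 1; that is inferred from the design.

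**5. What the 2-log rule would do if an on-drug sample were its baseline.** The documents give no size for the early fall in HBV DNA, so a fall of 0 to 3 log is an assumption. The threshold is the baseline plus 2 log. With a true baseline of 5 log, it is 7 log with no fall and 6, 5 or 4 log after a fall of 1, 2 or 3 log. If DNA becomes undetectable, the fixed 3-log limit applies instead: a 3-log baseline moves from 5 to 3, and a 1.5-log baseline from 3.5 to 3.

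**The case against.** A reader might infer that the reactivation comparison between Arms 1 and 2 is biased because antivirals lower the Arm 1 threshold. The documents do not support that. Section 5.3b requires an HBV DNA result, which it calls baseline, before registration, when Section 5.2f allows no HBV antiviral, and its source report is uploaded on the baseline form. Section 5.3a does the same for HBsAg, which covers seroreversion. The use of central results quoted above is translational. What stands against the plan is only that Section 10.2a does not name its comparator.

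A reader might also infer that baseline values differ by arm throughout. They need not. Part of the window precedes registration. In Cohort 2, Arm 3 treats on reactivation and Arm 4 at the physician's discretion, so there is no scheduled difference. Arm 1 is outside the case-control study, which the plan calls exploratory. Steady state is documented for entecavir only, and it measures drug level, not viral or immune response.

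It is also fair that 42 of the 70 days come from eligibility, that the 15-day deadline may shorten the window, and that collection dates on specimen labels would let late samples be flagged at analysis. But no such rule is written. The planned landmark analyses condition on surviving without reactivation; they do not separate pre-treatment from on-treatment samples. A pre-treatment sample not drawn in time cannot be recovered.

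**Conclusion.** The point holds for the translational analyses. Followed as written, the window allows on-treatment samples to be used as baseline: up to 28 days on antiviral in Arm 1, and up to 70 days into anti-cancer therapy in any arm (15 and 57 days if Section 14.4a binds). The case-control study is open to the anti-cancer exposure only; the Cohort 1 Cox models are open to both.

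These are maxima. They assume the latest permitted registration and draw and, for the antiviral figure, a start on the day of registration. The documents do not show how many samples would be late or how far any marker would move.

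The primary endpoint, sample size and power are untouched. The reactivation endpoint is protected from study-antiviral exposure if Section 5.3b supplies the comparator. That value is not necessarily free of anti-cancer exposure, since registration may follow the first cycle. This is an inexpensive improvement worth making, not a threat to the main comparison.

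**What to change.** 1. **Sections 15.1a.1 and 15.2a.1.** Require the first draw within 4 weeks before registration, or after registration (keeping the present four-week outer limit) but before the first protocol antiviral dose and, if anti-cancer therapy has not begun, before its first dose. This governs the draw only, not when treatment starts.
2. **Sections 14.4a and 18.1.** Reconcile the 15-day deadline and the four-week tolerance with the new wording.
3. **Section 18.1.** State that a sample taken after the first antiviral dose is not used as baseline. Analyse first samples taken after anti-cancer therapy began separately, or adjust for days since the first anti-cancer dose, using recorded collection dates.
4. **Section 10.2a.** Name the pre-registration HBV DNA of Section 5.3b as the baseline for the 2-log rule in all arms.

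**Effect.** Antiviral exposure at baseline falls from a maximum of 28 days to 0. Anti-cancer exposure falls to 0 for patients registered before therapy. For those registered after it began, exposure remains and item 3 handles it; even a rule confining the draw to on or before registration would lower that maximum only from 70 to 42 days.

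**Cost.** Protocol wording and one analysis rule, with no new draws and no change to sample size or power. A few first samples will be missed or reclassified.

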15.2 Whole Blood Specimens (**OPTIONAL for Patient**)

- a. With patient's consent whole blood specimens for intracellular cytokine staining (ICC), ELISA, IFN-gamma elispot testing (submitted to the SWOG Biospecimen Bank – Solid Tissue, Myeloma, and Lymphoma Division, Lab #201) must be submitted at the following time points (see [Section 9.0](#)).
 1. At time of registration (+/- 4 weeks)
 2. 8-12 weeks from registration
 3. 24 weeks (+/- 4 weeks) from date of registration
 4. At time of HBV-re-activation
- b. At each time point, a total 50 mL of blood will be drawn into five to eight purple top (EDTA) tubes using institutional supplies. Blood should be shipped the day of collection, overnight at ambient temperature. Blood may be shipped on Monday through Friday for Tuesday through Saturday delivery. If shipping for Saturday delivery, please mark Saturday delivery and notify the Bank. See [Section 15.3](#) for specimen shipment instructions.

15.3 SHIPPING SAMPLES

All specimens for this protocol should be shipped as Category B Infectious Substances.

- a. Specimen Labeling

Liquid specimens must be labeled with the following:

- SWOG patient number
- Patient initials
- Collection date (date the specimen was collected from the patient)
- Specimen type (e.g., blood, serum, etc.)

b. For additional information about labeling and shipping instructions (including address) refer to the SWOG Specimen Submission webpage (<https://www.swog.org/clinical-trials/biospecimen-resources/biospecimen-processing-and-submission-procedures>).

c. SWOG Specimen Tracking System (STS)

All specimen submissions for this study must be entered and tracked using the SWOG online Specimen Tracking system. SWOG members may log on the online system via the CRA Workbench. To access the CRA Workbench, go to the SWOG Web site (<http://swog.org>). Non- SWOG users may log into SpecTrack using their CTSU UserID and password on the SpecTrack login page located at <https://spectractr.crab.org> (select the option "SWOG – SWOG – CTSU". SpecTrack start-up instructions (both written and demo) are available after signing in to SpecTrack.

A copy of the Shipment Packing List produced by the online Specimen Tracking system should be printed and placed in the pocket of the specimen bag if it has one, or in a separate resealable bag.

ALL SPECIMENS MUST BE LOGGED VIA THIS SYSTEM; THERE ARE NO EXCEPTIONS.

(NOTE: If a specimen had an incomplete submission, this must be documented in the Specimen Tracking System under "Special Instructions" at time of specimen submission. If no specimen was available, this must be documented in the Specimen Tracking System by choosing "Notify that Specimen Cannot be Submitted").

To report technical problems with Specimen Tracking, such as database errors or connectivity issues, please send an email to [contact]. For procedural help with logging and shipping specimens, there is an introduction to the system on the Specimen Tracking main page (<https://spectractr.crab.org/Instructions>); or contact the SWOG Statistics and Data Management Center at [name] to be routed to the Data Coordinator for further assistance.

In the online specimen tracking system, the appropriate SWOG laboratory for submission of tissue and blood samples for SWOG Biospecimen Bank Submission is identified as follows:

Lab #201: SWOG Biospecimen Bank
Solid Tissue, Myeloma, and Lymphoma Division
[contact]
[contact]
E-mail: [contact]
